### **10.5 Final Analysis Plan**

Cardiopulmonary data – .shrd file type – from the ANNE Vital Sign System will be downloaded locally by Sunnybrook Research Institute (SRI) who will convert to .edf file type, and manually annotate to extract information on sleep apnea. SRI will then upload processed data to the Longitudinal Online Research and Imaging System120 (LORIS). All uploads and downloads will be by Secure File Transfer Protocol (SFTP). We will quantify the apnea hypopnea index (AHI), oxygen desaturation index (ODI), hypoxemia burden, and time with oxygen saturation below 90% (O2<90). In addition, we will quantify 24-hour resting heart rate, and average heart rate, which are important physiological consequences of sleep apnea. Participants will be considered to have sleep apnea if their AHI is greater than or equal to 15. We will relate the presence of sleep apnea to change in MoCA scores between baseline and 12 months using t-tests. We will then use mediation analyses to test if any observed associations are mediated by effects of sleep apnea on average and daytime resting heart rate. Sex-stratification will be used in analyses as appropriate.

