### **3 STUDY OBJECTIVES**

#### **3.1 Primary Objective**

The primary objective of this study is to test the hypothesis that sleep apnea is associated with accelerated cognitive decline in older adults at risk for dementia. We will measure sleep apnea at baseline and 12 months later and relate this to cognitive function at the same time points.

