## 4 STUDY DESIGN

### 4.1 General Design

The Canadian Therapeutic Platform Trial for Multidomain Interventions to Prevent Dementia (CTU) is a Canada-wide study of older adults at risk for dementia, undertaken by the Canadian Consortium on Neurodegeneration that will begin recruitment in May 2022 and is anticipated to recruit 750 participants from May 2022-April 2024. The main goal of the CTU study is to serve as a shared platform to support studies of technologies and interventions to prevent dementia. These sub-studies are able to share CTU resources for recruitment and outcome ascertainment.

Participants in CTU and affiliated studies will be invited to participate in the ANNE Vital Sign System sub-study. CTU recruiting sites will refer potential participants to Sunnybrook Research Institute (SRI) to obtain informed consent and then prepare shipment of ANNE Vital Sign System and instructions to participant. The informed consent process will be conducted according to sections 7.1 and 13.3 of this protocol. After study equipment and materials are shipped to and received by the participant, study staff will instruct the participant on the proper application and use of the ANNE Vital Sign System over remote video-conference. Specifically, study staff will instruct the participant to affix the ANNE Vital Sign System chest sensor to the participant's chest using electrode paste, the ANNE chest adhesive, and Tegaderm or similar. Study staff may ask participants to shave a 3"x2" section of their chest, but participants will be informed this is optional. Next, study staff will instruct the participant to affix the ANNE Vital Sign System finger sensor to the participant's non-dominant index finger using the ANNE limb adhesive. Participants will wear the sensors for 24 hours before removing it themselves at home and shipping back to Sunnybrook Research Institute using a pre-paid, pre-addressed package. This procedure will be completed at the Baseline visit and repeated 12 months later.

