## 5 PARTICIPANT SELECTION AND WITHDRAWAL

All individuals enrolled in CTU and affiliated studies will be eligible to complete the ANNE Vital Sign System sleep assessment unless excluded by an additional set of exclusion criteria specific to the ANNE Vital Sign System. CTU recruitment is aiming to recruit 50% women to allow for later stratification of analyses to assess for sex differences.

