### 5.2 Exclusion Criteria

The exclusion criteria for this study are:

1. Known nickel allergy
2. Known cardiac implantable device
3. Known arrhythmias

4. Otherwise unable to use the sensors; for example, finger amputations

For reference, exclusion criteria of CTU affiliated studies from which we will recruit may include, but are not limited to, the following list:

1. Participants who, in the opinion of the investigator, are not able to complete trial procedures remotely or adhere to the schedule of study assessments.
2. Individuals where English or French is not sufficiently proficient for remote clinical assessment.
3. Individuals who do not have the technical ability. Technical ability is defined as having computer and internet access; ability to send and receive emails; ability to participate in remote assessments.
4. Individuals who have a clinical diagnosis of Dementia
5. Clinical Dementia Rating (CDR; telephone/video-conference administration) Score of  $\geq 1$  or having a diagnosis of dementia based on DSM-IV criteria
6. Total Score on the Montreal Cognitive Assessment (MoCA; video-conference administration)  $< 13$

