## **7.3 Study visits/Follow up**

Baseline procedures will be repeated 12 months later. Participants at either time point with an AHI of  $\geq 15$  as determined by our quantification will be called via telephone by study staff to be a) notified that they have a high probability of having sleep apnea and if accompanied by severe sleepiness should refrain from driving, b) encouraged to contact their family physician for clinical evaluation where an official diagnosis of sleep apnea may or may not be made, and c) asked to notify study staff if they obtain treatment, unless treatment is obtained after their month 12 visit. Participants will be reminded that data collected as part of this study are for research purposes only and may not constitute a diagnosis of sleep apnea.

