## **10 STATISTICAL CONSIDERATIONS**

### **10.1 Study Hypotheses**

We hypothesize that participants with sleep apnea will have a greater 12-month change in their Montreal Cognitive Assessment scores than those without

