### **10.2 Sample Size Considerations**

We anticipate that ~30% of participants (i.e. 210 participants) will have sleep apnea. Based on this, we estimate 86% power to detect a ~0.5 point difference in 12-month change in MoCA between participants with and without sleep apnea. As it is possible that treatment of sleep apnea may be a potential source of noise regarding longitudinal cognitive outcomes, we will adjust for this statistically by collecting information on treatment and adjusting as a covariate.

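### The treatment adjustment promised in section 10.2 has no model to carry it, because section 10.5 names only t-tests, and apart from discretionary sex stratification nothing at baseline is adjusted for.

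*Combined protocol and SAP*

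**What the plan says.** The study is a prospective cohort (Protocol Summary), so apnea, defined as an AHI of 15 or more, is observed and not assigned.

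- **Analysis.** Section 10.5, and section 4.2 in the same words: "We will relate the presence of sleep apnea to change in MoCA scores between baseline and 12 months using t-tests". Mediation analyses through heart rate follow, with no model form or covariates. The Statistical Analysis entry of the Protocol Summary names no test.
- **Hypothesis.** Section 10.1: "We hypothesize that participants with sleep apnea will have a greater 12-month change in their Montreal Cognitive Assessment scores than those without".
- **Treatment.** Section 10.2 calls treatment of apnea a possible source of noise and says "we will adjust for this statistically by collecting information on treatment and adjusting as a covariate". The only collection described is in section 7.3: participants telephoned because their AHI is 15 or more are "asked to notify study staff if they obtain treatment, unless treatment is obtained after their month 12 visit". Treatment already in use at baseline is not among the exclusions in section 5.2.
- **Baseline characteristics.** Only sex is mentioned, by stratification where appropriate (sections 3.2, 4.3 and 10.5). Section 5 supports it: "CTU recruitment is aiming to recruit 50% women to allow for later stratification of analyses to assess for sex differences".
- **Timing of exposure.** Section 3.1: "We will measure sleep apnea at baseline and 12 months later and relate this to cognitive function at the same time points". Sections 4.2 and 10.5 do not say which recording defines the groups.

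**The concern.** There are two gaps.

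First, section 10.2 commits to an adjustment that the analysis section cannot perform. Filling the gap takes more than wording, because the treatment term may change the question. The hypothesis compares everyone with apnea with everyone without it. A model with treatment recorded only in the apnea group compares untreated apnea with no apnea. If this stays open, the choice of model, and of the comparison reported, could be made after the data are seen. Nor can a reader tell which model the 86% power describes.

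Second, the crude difference describes an association, which is what the objective in section 3.1 asks for. It cannot separate apnea from age, BMI or parent study where these are related to 12-month change. Participants come from several affiliated studies on a platform meant to "serve as a shared platform to support studies of technologies and interventions to prevent dementia", so parent study matters if the studies differ in both apnea prevalence and MoCA change. Stable differences in MoCA level cancel in a change score; only characteristics related to change matter. The mediation step is worded in terms of the effects of apnea, and an unadjusted model cannot support that reading.

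**Working it through.** **Inputs from the documents.** Total 750 (Protocol Summary, section 5.3); about 30% with apnea, given as 210; difference 0.5 points; power 86% (section 10.2).

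**Assumptions.** The SD, alpha, sidedness and dropout are not stated. I use a two-sided 5% level, no dropout and a back-solved SD. For group sizes, 210 is 30% of 700, which leaves 490; but 750 - 210 = 540, and 30% of 750 is 225. I use 210 and 490 and give the effect of 540.

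**1. The plan's own figure.** By the noncentral t, 86% power needs an SD of 1.99 (210/490), 2.02 (210/540) or 2.06 (225/525). With SD 2.0, SE = 2.0 × √(1/210 + 1/490) = 0.165 and power for 0.5 points is 85.7%. With 540 it is 86.7%. So 86% is attainable for an unadjusted two-group comparison, but cannot be confirmed without the SD and alpha.

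**2. What the treatment term does.** Write change = a + b × apnea + c × treated. If treatment is recorded only within the apnea group, there are three groups and three parameters. Then b is the mean in untreated apnea minus the mean in no apnea, with SE = 2.0 × √(1/n_untreated + 1/490).

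For the t-test, the expected difference is 0.5 × (1 - q × k), where q is the share treated and k the fraction of the effect that treatment removes. Both are assumed.

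| Share treated (q) | Untreated n | SE with treatment term | Power with treatment term | t-test, k = 0.5: difference; power | t-test, k = 0.25: power |
|---|---|---|---|---|---|
| 10% | 189 | 0.171 | 83.0% | 0.475; 82.0% | 84% |
| 30% | 147 | 0.188 | 75.6% | 0.425; 73.0% | 80% |
| 50% | 105 | 0.215 | 64.1% | 0.375; 62.2% | 75% |

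With 540 in place of 490, the figures are about 1 point higher.

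**3. Confounding, illustration only.** For one covariate, bias = imbalance in SD units × correlation with change × 2.0. No input comes from the documents. Imbalance of 0.3-0.6 SD and correlation of 0-0.2 give:

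- correlation 0: bias 0, rejection 5.0% when apnea has no effect;
- 0.3 × 0.1 × 2.0 = 0.06 points: 6.5%;
- 0.6 × 0.1 × 2.0 = 0.12 points: 11.2%;
- 0.6 × 0.2 × 2.0 = 0.24 points: 30.6%.

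**4. Price of adjustment.** With 30% exposed, an imbalance of d SD means the covariate explains 0.21d²/(1 + 0.21d²) of exposure variance (0.21 = 0.3 × 0.7): 1.9% at d = 0.3 and 7.0% at d = 0.6. The SE is multiplied by √((1 - R²_outcome)/(1 - R²_exposure)). If the covariates explain no outcome variance, power is 85.1% at 1.9%, 83.1% at 7.0% and 81.9% at 10%. If they explain as much outcome as exposure variance, power stays at 85.7%; if more, it rises.

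**The case against.** The strongest reply is that nothing here is contradictory. Section 10.2 does not say that the treatment covariate belongs to the primary test, and section 10.5 does not say that t-tests are the only analysis. The text fits an unadjusted t-test plus an adjusted analysis yet to be described. This stands: a reader might infer two rival primary analyses, and the documents do not establish that. What they do establish is an omission, a promised adjustment with no analysis to hold it.

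On confounding, the objective speaks of association, and a crude difference answers it. Sex is handled, if only at discretion. No passage links age or BMI to AHI or to MoCA change; section 5.1 lists BMI above 30 only as one possible entry criterion of the parent studies. This also stands. The 31% rejection rate is the extreme corner of an assumed grid and no evidence of harm.

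A reader might also infer that the treatment model should be secondary because it loses power. The figures do not support that. If treatment halves the effect, the t-test has less power than the treatment model at every share shown; if treatment removes a quarter, it has more. The sound reasons are that treatment follows the exposure and that the term changes the comparison.

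Finally, section 10.2 does not limit treatment data to participants with an AHI of 15 or more. That restriction is read from section 7.3, so the change of comparison is conditional on it.

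**Conclusion.** The point holds as an omission in the analysis plan. That a t-test cannot hold the covariate promised in section 10.2, and that no other model is named, follows from the text alone and needs no assumption. That the treatment term turns the comparison into untreated apnea versus no apnea holds if treatment is recorded only as section 7.3 describes.

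The size depends on assumptions: two-sided 5%, SD 2.0, 210 versus 490. With 10-50% of the apnea group treated, power for 0.5 points is 83-64% with the treatment term. For the t-test it is 82-62% if treatment halves the effect and 84-75% if it removes a quarter. The 86% is therefore secure for neither analysis if treatment is common and works.

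The lack of baseline adjustment limits interpretation: a crude difference cannot be read as apnea rather than its correlates. Whether the resulting bias is negligible or serious, and in which direction, cannot be told from the documents. A reader should not conclude that the result would be confounded, only that the plan has no means of checking.

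**What to change.** 1. **Sections 4.2 and 10.5.** Make the primary analysis a linear regression of 12-month MoCA change on AHI of 15 or more at the baseline recording. Prespecify a fixed covariate list (age, sex, BMI, parent study), confirmed as available before analysis, with a stated rule for missing covariate values. Report the adjusted difference with its 95% CI. Keep the t-test as the labelled unadjusted companion. Omit the sex term in sex-stratified models.
2. **Mediation.** Use the same baseline covariates in the mediation models.
3. **Treatment.** Carry the section 10.2 adjustment into section 10.5 as a labelled sensitivity model, and state that its main coefficient is untreated apnea versus no apnea. Record treatment for all participants at the existing calls. Use exhaustive groups: no apnea; apnea untreated; apnea with treatment begun after notification; and already treated at baseline, whatever the AHI. Repeat the primary analysis without the last group.
4. **Section 10.2.** State the SD, the alpha and which model the 86% refers to.

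**Cost.** Wording in three sections and one added question; no new visit or participant. The team must confirm that the parent studies can supply the covariates. Section 5.1 gives their criteria only for reference, and risk factors there, BMI among them, may be self-reported or date from midlife. Some values will be missing. Power falls from 86% to about 85-82% if the covariates explain 2-10% of exposure variance and no outcome variance. It is unchanged or better if they explain at least as much outcome variance.

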## **11 DATA HANDLING AND RECORD KEEPING**

### **11.1 Confidentiality**

Information about study participants will be kept confidential and managed according to the requirements of the Personal Health Information Protection Act of 2004 (PHIPA) and the Research Ethics Board. PHIPA outlines the rules for the collection, use and disclosure of personal health information. The Act requires each participant to consent to the collection, use and access of personal health information (PHI), unless consent is waived by the REB. Where consent is required, each participant must be informed of the following:

- What PHI will be collected during this study
- Who will have access to that information and why
- Who will use or disclose that information
- The rights of a research participant to revoke their authorization for use of their PHI.

In the event that a participant revokes authorization to collect or use PHI, the investigator may use all information collected prior to the revocation of participant authorization. For participants that have revoked authorization to collect or use PHI, attempts should be made to obtain permission to collect at least vital status (i.e. that the participant is alive) at the end of their scheduled study period.

### **11.2 Source Documents**

Source data/documents are original documents, data and records in a clinical study that are necessary for the reconstruction and evaluation of the study. Examples of these original documents and data records include, but are not limited to:

- worksheets
- hospital records
- medical records
- memorandum
- participants' diaries or evaluation checklists
- recorded data from automated instruments (i.e. ECGs)
- copies or transcriptions certified after verification as being accurate and complete
- entries entered directly into the printed CRF

### **11.3 Data Management Responsibilities**

Data collection and accurate documentation are the responsibility of the study personnel under the supervision of the investigator. All source documents should be reviewed as needed and used to ensure that data collected for the purposes of the study are accurate and complete. Study personnel, including data entry team members, should use source documents to complete case report forms (CRFs).

As part of the safety plan for this study, the investigator will review individual study participant records to ensure that appropriate mechanisms to protect the safety of study participants are being followed, that protocol requirements are being adhered to, and that data is accurate, complete, and secure. Participant records include, but are not limited to: consent forms, case report forms, and data forms. All study data will be collected by a member of the study research team and recorded in accordance with applicable procedures.

## **11.4 Data Capture**

### **11.4.1 Case Report Forms**

The study case report form (CRF) is the primary data collection instrument for the study. Electronic/Paper case report forms (eCRFs/pCRFs) will be used to collect data for this study. CRFs are to be completed by data capture personnel and signed off by the investigator in a timely manner. Good documentation practices should be implemented according to standard operating procedures. All data requested on the CRF must be recorded and verifiable by source document.

## **11.5 Records Retention**

*It is the responsibility of the REB, investigator and regulatory sponsor to retain study essential documents as per local regulatory requirements and GCP Guidelines.*

Study essential documents must be maintained in a secure and confidential manner for participating Canadian sites for a period of 25 years. For the purposes of this study, the start date of the retention period is the date of the final report of the trial. Exceptions may be made for sites which close prematurely, wherein the start date for the retention period will be the date of notification to Health Canada of the sites closure. Sites conducting this study outside of Canada must maintain study records for the required retention period as stipulated by local regulatory authorities. All study records are then to be destroyed according to local and national policy and requirements. It is the investigator's responsibility to request authorization for destruction at the completion of the retention period and/or for the sponsor to inform the investigator/institution when these documents may be destroyed.

## **11.6 Clinical Trial Registration**

In accordance with Health Canada's Notice "Registration and Disclosure of Clinical Trial Information, November 30, 2007", the sponsor will be responsible for registering the study on Clinicaltrials.gov ([www.clinicaltrials.gov](http://www.clinicaltrials.gov)), a publically available registry that conforms to international standards for registries.

## 12 QUALITY CONTROL AND QUALITY ASSURANCE

As per ICH-GCP and local regulations, the sponsor is responsible for ensuring the implementation and maintenance of systems that support quality assurance and quality control.

The study must be conducted in compliance with the study protocol and all data collected must be accurate and verifiable by source document(s). For the purpose of monitoring and auditing by the Sponsor, and inspection by regulatory authorities, the site will provide direct access to all study related source data/documents. The sponsor will verify that the study is conducted and data has been collected, documented (recorded), and reported in compliance with the protocol, GCP, and applicable regulatory requirements.

Access to secure and validated electronic systems used for the purposes of this study will be controlled by the sponsor. Access will only be granted to individual research team members upon review of training and qualification and authorization by delegation of the investigator.

Quality assurance and control measures will be implemented to ensure training for specific trial-related tasks beyond the usual scope of practice. Only procedures or interventions as outlined in section 6.1, are considered study specific procedures requiring additional training, and will be reviewed for documentation of training and/or qualification.

For the purposes of this study, “research device” is defined as device used solely for the purposes of this study and that are unrelated to the delivery of standard-of-care treatment or procedures. In accordance with this definition, performance verification and /or calibration documentation will only be maintained for the following pieces of research device:

- ANNE Vital Sign System

## **13 ETHICS CONSIDERATIONS**

### **13.1 Ethical Standard**

The investigator will ensure that this study is conducted in accordance with the principles set forth in The Belmont Report: Ethical Principles and Guidelines for the Protection of Human Participants of Research, and codified in the Tri-Council Policy Statement and/or the ICH E6.

### **13.2 Research Ethics Board (REB)**

The protocol, informed consent form(s), recruitment materials, and all participant materials will be submitted to the REB for review and approval. Approval of both the protocol and the consent form must be obtained before any participant is enrolled. Any amendment to the protocol will require review and approval by the REB before the changes are implemented in the study, unless to eliminate an immediate hazard.

